### 5.2.2 *Baseline Visit*

The baseline visit will occur within 0-14 days of the screening visit. If laboratory studies are obtained at the screening visit, results must be reviewed prior to the baseline visit. Participants will be randomized to one of two treatment groups. Participants will be randomized to group according to a computer-generated randomization scheme. Based on this randomization, study personnel will be informed which drug bottles to supply the participant. The first dose of study drug or placebo should be taken the following morning.

Evaluations:

- Demographics
- Health Update
- Concomitant Medications
- NINDS Common Data Elements PD Medical History
- MDS-UPDRS
- Vital Signs
- Unified Dyskinesia Rating Scale
- Parkinson Anxiety Scale
- Hamilton Anxiety Scale

- Hospital Anxiety and Depression Scale

**5.2.3 Visit 01 (Day 14 +/- 3 days), Visit 02 (Day 28 +/- 3 days), Visit 03 (Day 56 +/- 3 days), and Visit 04 (Day 84 +/- 3 days)**

Visit 01, Visit 02, Visit 03, and Visit 04 should occur within 3 days of the target date. Previously dispensed study drug bottles will be collected and new study drug bottles dispensed at each visit.

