## **7.0 PARTICIPANT WITHDRAWALS**

Participants will be advised in the written informed consent forms that they have the right to withdraw from the study at any time without prejudice. Participants may be withdrawn by the investigator/sponsor for:

- (1) Non-compliance with study drug or procedures
- (2) Receipt of disallowed medications that cannot be discontinued
- (3) An adverse event which in the investigator's judgment puts the participant at risk
- (4) Illness that prevents continued trial participation
- (5) Termination of study funding
- (6) Worsening of anxiety that in the investigator's judgment requires prompt treatment with an alternative therapy

In the event of a premature study withdrawal, a premature termination visit should occur. Evaluations are detailed in section 5.2.6. Participants withdrawn from the study will not be replaced.

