## **13 DATA ANALYSIS AND MONITORING**

### **13.1 Sample Size Determination**

The primary outcome for tolerability is the proportion of participants who fail to complete the 12-week study on study drug (intolerability). This study uses a single-

arm futility design to determine the tolerability of buspirone by comparing the observed intolerability rate ( $\theta_E$ ) against an intolerability rate that would be unacceptably high ( $\theta_O$ ). 20% represents a reasonable value for unacceptably high intolerability ( $\theta_O$ ). Our null hypothesis is that buspirone is tolerable and  $\theta_E \leq \theta_O$ . Our alternative hypothesis is that buspirone is intolerable and that  $\theta_E > \theta_O$ . A sample size of 21 will provide 80% power to reject the null hypothesis of tolerability (observed intolerability  $\leq 20\%$ ) in favor of the alternative hypothesis of intolerability (observed intolerability  $> 20\%$ ) if the true intolerability is greater than 40%, using a binomial test and a one-tailed significance level of 10% significance. With the introduction of a placebo arm for blinding and relying on a 4:1 allocation ratio, the desired sample size increases to 27. We are willing to accept a higher chance that we declare an intolerable drug tolerable as the expected intolerabilities (headache, nausea, drowsiness, dizziness, and temporary worsening of PD motor function) are not expected to be serious and could be confirmed in larger studies. We are more concerned about declaring a truly tolerable drug intolerable and not moving forward with larger studies.

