### 13.2 Planned Statistical Analysis

The primary outcome for tolerability is the proportion of participants who fail to complete the 12-week study on study drug, as described in **Sample Size and Accrual**. The number of participants who fail to complete the study on study drug will be determined and if 7 or more participants fail to tolerate the study drug, the null hypothesis will be rejected. Participants who do not complete the study on study drug for any reason will be considered as experiencing intolerability for purposes of the primary analysis.

As a secondary analysis we will calculate the number of participants who fail to complete the study on study drug due to adverse events; separating them from those who fail to complete the study on study drug for alternative reasons. We will also calculate the number of participants who required dosage reductions during the study and use descriptive statistics to describe the average study drug dosage and dosage reductions.

Safety analyses will include tabulating adverse events by treatment group and severity and codifying the relationship to study drug. Serious adverse events attributable to buspirone treatment will be described in detail. Adverse event incidence will be summarized along with the corresponding 95% two-sided confidence interval. The mean change in MDS-UPDRS motor score and from baseline to 12 weeks will be calculated. We will use descriptive statistics to characterize the range and variability of study drug dosages.

Secondary outcomes related to anxiety will include the mean change in HAM-A score from baseline to 12 weeks, mean change in HADS score from baseline to 12 weeks and the proportion of participants "much improved" or "very much improved" on CGI-I, proportion "much improved" or "very much improved" on PGI-I, and proportion of responders ( $> 50\%$  reduction from baseline or reduction to  $\leq 7$  in HAM-A) at 12 weeks. The secondary outcome regarding levodopa-induced dyskinesias will be the mean change in UDysRS score from baseline to 12 weeks. Similar analyses will be done for all outcomes at 2 weeks, 4 weeks, and 8 weeks. For participants lost to follow up, the

last observation carried forward will be used. We will also correlate mean change in the Parkinson Anxiety Scale scores with mean change in the CGI-I and PGI-I scores.

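### The any-reason failure rule would score a study-level stop, such as loss of funding, as buspirone intolerability, and a stop late in accrual could materially raise the chance of wrongly rejecting tolerability

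*Combined protocol and SAP*

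**What the plan says.** The primary outcome is the proportion who do not complete 12 weeks on study drug. Section 13.2 sets the scoring, "Participants who do not complete the study on study drug for any reason will be considered as experiencing intolerability", and the decision: "if 7 or more participants fail to tolerate the study drug, the null hypothesis will be rejected".

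Section 13.1 gives the design behind that cut-off. "A sample size of 21 will provide 80% power to reject the null hypothesis of tolerability", "using a binomial test and a one-tailed significance level of 10% significance", with a null limit of 20% and a true rate of 40% as the alternative. The same section says the sponsor is more worried about calling a tolerable drug intolerable than about the reverse error.

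Section 7.0 lists the grounds on which the investigator or sponsor may withdraw a participant. Most concern the participant: non-compliance, disallowed medication, an adverse event, illness, worsening anxiety. One does not: "5) Termination of study funding". Withdrawn participants are not replaced.

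Section 13.2 also plans a secondary count of failures due to adverse events, kept apart from other reasons. Section 2.4 assumes a placebo intolerability rate of zero and uses the small placebo arm to check it.

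**The concern.** Counting every participant-level reason as a failure is a defensible conservative choice, because the drug may have contributed to any of them. A closure for lack of funding is different. It reaches everyone on treatment that day, whatever their experience, and carries no information about buspirone. Read together, 13.2 and 7.0 nevertheless turn each of them into an intolerability.

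The decision rests on 7 failures among about 21 people, with an assumed background rate of zero and no dropout allowance, so a few automatic failures use up much of the margin. The error they inflate, declaring a tolerable drug intolerable, is the one 13.1 says matters more.

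**Working it through.** **Inputs from the documents.** Planned buspirone sample 21, null rate 20%, alternative 40% (13.1); cut-off 7 (13.2); total 27 with 4:1 allocation (13.1); recruitment over 24 months (4.1); 12 weeks of treatment.

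**Assumptions.** Failures are independent. The 7 are counted in the buspirone arm, which 13.2 does not say outright. Accrual of 27 is even over the 24 months. (Section 4.1 attaches the 24 months to 35 participants, and 3.1 says 35 includes screen failures.)

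**Step 1: reproduce the design.** With X binomial(21, p):
- power: P(X ≥ 7 | p = 0.40) = 0.7998, matching the stated 80%
- type I error: P(X ≥ 7 | p = 0.20) = 0.1085, slightly above the stated 10%

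**Step 2: how many would a stop catch?** 24 months is about 104.4 weeks. On treatment at once during accrual: 27 / 104.4 × 12 = 3.1 people, and 3.1 × 0.8 = 2.5 on buspirone. Two or three automatic failures is the typical number.

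**Step 3: effect at full accrual.** If k of 21 are automatic failures, the other 21 − k must supply 7 − k:

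P(reject) = P(X ≥ 7 − k), X binomial(21 − k, p).

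For example, k = 2 at p = 0.20 is P(X ≥ 5 | n = 19) = 0.327.

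| True rate | k = 0 | k = 1 | k = 2 | k = 3 |
|---|---|---|---|---|
| 10% | 0.3% | 1.1% | 3.5% | 9.8% |
| 15% | 2.9% | 6.7% | 14.4% | 28.0% |
| 20% | 10.9% | 19.6% | 32.7% | 49.9% |

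**Step 4: effect of an earlier stop.** Same formula, true rate 20%, cut-off still 7, with m randomised to buspirone in place of 21:

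| m | k = 2 | k = 3 |
|---|---|---|
| 10 | 1.0% | 3.3% |
| 14 | 7.3% | 16.1% |
| 16 | 13.0% | 25.3% |

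The large values in step 3 therefore belong to a stop around the end of enrolment. Earlier, fewer have been randomised; later, fewer are still on treatment, and with one left the figure is 19.6%.

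**Step 5: could the stop alone reach 7?** It would have to catch 7 on buspirone at once. With a Poisson number on treatment, mean 21 × 12 / 104.4 = 2.4, that has probability about 1.2%, given a stop. If 28 were randomised to buspirone (35 × 0.8), the mean is 3.2 and the probability about 4.6%.

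**The case against.** The best defence is that the any-reason rule is stated openly, applied consistently and conservative by design. Reasons for premature withdrawal are documented (5.2.6), and the secondary adverse-event count in 13.2 would let a reader see a funding stop and separate it out. The placebo arm offers some check on the background rate. All of this stands and helps interpretation, but none of it alters the primary decision, which still turns on the any-reason count.

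A second objection is that a funding stop is a contingency to which the documents attach no probability, and that a stop midway would leave the planned 21 unmet, a larger problem than scoring. This also stands. It limits the point to a stop late in accrual and makes every figure conditional.

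A reader might go further and infer that such stops could by themselves carry a tolerable drug past the cut-off. The documents do not support that: two or three automatic failures are not seven, and step 5 shows that seven at once is improbable even given a stop.

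A reader might also infer that randomised participants who never take a capsule are misclassified in the same way, since under 5.2.2 "The first dose of study drug or placebo should be taken the following morning". The documents do not mention such participants. Deciding not to start is a participant-level reason, the kind it is defensible to count. Excluding these people would be a debatable change of analysis set, and the only principle the protocol names is intention to treat (8.6, for unblinded participants).

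**Conclusion.** The concern holds in a limited form. As written, 13.2 and 7.0 together score a study-level administrative stop as intolerability. The effect is additive. For a stop near the end of accrual with 2 or 3 of 21 still on buspirone, false rejection at the 20% limit rises from 10.9% to 32.7% or 49.9%. At a true 10% rate it rises from 0.3% to 3.5% or 9.8%. With 10 to 14 randomised it is about 1% to 16% at a true 20% rate.

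These are not the trial's overall error rates. They are conditional on a funding stop and rest on even accrual, independent failures and a count confined to the buspirone arm. What makes the point worth acting on is that the misclassification is certain if the event occurs, runs in the direction the sponsor most wants to avoid, and can be prevented with a few sentences.

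**What to change.** Amend 13.2 before unblinding, so that the carve-out cannot look result-driven:

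- Keep every participant-level reason as a failure, including not starting study drug after randomisation.
- Remove from the numerator and denominator of the primary analysis only participants whose sole reason for not completing was a study-level administrative stop (funding or site closure), as judged blind to arm.
- State the boundary for a reduced denominator. One workable criterion is the smallest count whose exact one-sided error at 20% does not exceed P(X ≥ 7 | n = 21, p = 0.20), the 10.85% the plan already accepts. Define it by that expression, because the unrounded value (0.10851) is just above 10.85%. It keeps 7 for 18 to 21 evaluable. A strict 10% ceiling would instead require 8 of 21, with error 4.3% and power 65.0% even when nobody is removed.
- Report the all-randomised, any-reason count as a sensitivity analysis.

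The cost is a change of wording and, only if a stop happens, lower power at a true 40% rate: 75.0%, 69.2% and 62.6% with 20, 19 and 18 evaluable, against 80.0% with 21. A small bias against the drug would remain, because recent recruits who had already failed stay in the count while those still on treatment are removed. The sensitivity analysis should be read with that in mind.

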SECONDARY OUTCOME MEASURE(S)	
Safety and Tolerability:
 
 
(1) Number and type of adverse events
 
(2) Number and type of serious adverse events
 
(3) Mean change in MDS-UPDRS motor from baseline to 12 weeks
 
(4) Mean change in calculated levodopa-equivalent dose from baseline to 12 weeks
 
 
Anxiety:
 
 
(1) Mean change in Hamilton Anxiety Rating Scale (HAM-A) from baseline to 12 weeks
 
(2) Proportion of responders (>50% reduction from baseline or reduction to ≤7 on HAM-A) at 12 weeks
 
(3) Proportion “much improved” or “very much improved” on Clinical Global Impressions-Improvement (CGI-I) and Patient Global Impressions-Improvement (PGI-I) at 12 weeks
 
(4) Mean change in Hospital Anxiety and Depression Scale (HADS) from baseline to 12 weeks
 
 
Levodopa-Induced Dyskinesias:
 
 
(1) Mean change in Unified Dyskinesia Rating Scale (UDysRS) from baseline to 12 weeks
 
 
Parkinson Anxiety Scale:
 
 
(1) Correlation of change with CGI-I and PGI-I
 

SAFETY CONSIDERATIONS	Bupirone is FDA-approved for treatment of generalized anxiety disorder. According to the package insert, in premarketing clinical efficacy trials, 10% of 2200 participants discontinued treatment secondary to an adverse event and in pooled analysis of placebo-controlled clinical trials the most common adverse events included dizziness (12%), drowsiness (10%), nausea (8%), headache (6%), nervousness (5%), fatigue (4%), insomnia (3%), lightheadedness (3%), and dry mouth (3%).

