### 2.2. Rationale for Study Design

The primary objective of this study is to determine the tolerability of buspirone in PD. The primary outcome is the proportion of participants who fail to complete the 12-week study on study drug. We hypothesize that  $> 20\%$  of participants will fail to complete the study on study drug. As the primary tolerability concern with buspirone that is specific to the PD population is worsening of motor function, we considered selecting mean MDS-UPDRS motor scale change from baseline to 12 weeks as the primary outcome for tolerability. This approach was rejected as it would not capture alternative reasons for intolerability (such as nausea, headache, or dizziness). The 12-week duration should provide adequate time for response to treatment and to assess any effect on PD motor function.

From the standpoint of sample size calculations and statistical analysis this is a single-arm futility design; a placebo arm is introduced to allow for blinding and calibration. The use of a futility design over a traditional design allows for higher sensitivity at the cost of lower specificity. In other words, the futility design increases the probability of declaring a truly tolerable drug tolerable (correctly failing to reject the null hypothesis of tolerability) at the cost of a decreased probability of declaring a truly intolerable drug intolerable (correctly rejecting the null hypothesis of tolerability). Given the importance of moving a therapeutic for anxiety through and as the expected intolerabilities (headache, nausea, drowsiness, dizziness, and worsening of PD motor function) are either not expected to be serious or expected to be reversible, and could be confirmed in larger studies, this is a favorable scenario.

The secondary exploratory objectives examining the efficacy of buspirone in reducing symptoms of anxiety and in reducing levodopa-induced dyskinesias were included to provide the opportunity to detect a signal of efficacy regarding potential therapeutic uses of buspirone in PD.

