### 5.4.5 Movement Disorders Society-Unified Parkinson's Disease Rating Scale (MDS-UPDRS)

The MDS-UPDRS has been previously validated, is increasingly being used in Parkinson's disease clinical trials, and is preferable over the UPDRS due to its ability to more finely discriminate degree of impairment. The minimally clinically important difference for improvement (-3.25) and worsening (4.63) on the MDS-UPDRS Motor was recently established. Investigators will be required to provide verification of their completion of the MDS-UPDRS certification course to ensure adequate inter-rater reliability. In order to minimize differences in scores attributable to the timing of Parkinson's disease medications, for participants who are on levodopa investigators will always attempt to administer the MDS-UPDRS Motor during the ON state (generally about 1 hour after levodopa administration). MDS-UPDRS Item 2.3 *Chewing and Swallowing* will be completed by the participant at the screening visit to screen for dysphagia that may result in difficulty swallowing the study drug and would preclude safe participation in the study. A score of  $\geq 2$  ("I need to have my pills cut or

my food specially prepared because of chewing or swallowing problems, but I have not choked over the past week”) will exclude the participant from the study. The full MDS-UPDRS, including Part 1: Non-Motor Aspects of Experiences of Daily Living, Part II: Motor Aspects of Experiences of Daily Living, Part III: Motor Examination, and Part IV: Motor Complications, will be administered by an investigator at the baseline visit and the participant will complete those aspects of the MDS-UPDRS covered in the patient questionnaire (items 1.7-1.13 and 2.1-2.13). The MDS-UPDRS Motor will be administered by an investigator at each subsequent in-person study visit.

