#### 5.4.7 *Adverse Events*

Soliciting of adverse events will be non-specific and participants will be asked the question, “Do you feel different in any way since starting the new treatment?” All adverse events occurring after the baseline visit will be reported. All subsequent adverse events will be reported regardless of relationship to drug.

At each in-person and telephone visit, a study coordinator will solicit adverse events. Adverse events not previously documented in the study will be recorded in the adverse event section in the case report form. The nature of each individual event, date and time of onset, duration, severity, and relationship to treatment will be established by the investigator. Likely alternative etiologies should be recorded for events considered unrelated to study drug. Details of change to the dosing schedule, any corrective treatment, or prescription of a concomitant medication, must be recorded on the appropriate pages of the case report form. We will use the UKU Side Effects Rating Scale, developed by the Committee on Clinical Investigations (Udvalg for kliniske undersøgelser, UKU), which is a standing committee under the Scandinavian Society of Psychopharmacology. Items in the UKU are sub-grouped into psychic, neurological, autonomic, and other categories. The cardinal PD symptoms of tremor, rigidity, and hypokinesia are included.

Adverse events already documented in the CRF, at a previous visit, and designated as ‘continuing’ should be reviewed at each visit. If an adverse event is resolved, the documentation in the CRF must be completed to that effect. If an adverse event changes in frequency or severity during a study period, a NEW record of that event will be initiated. A record of all adverse events will be reviewed periodically by the study investigators. The documentation and classification of adverse events is further reviewed in section 9.

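### The MDS-UPDRS motor score, the monitor for the main PD-specific concern, is summarised only by mean change, which can hide individual worsening beyond the cited 4.63 points

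*Combined protocol and SAP*

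**What the plan says.** Section 2.2 ranks the concern: "As the primary tolerability concern with buspirone that is specific to the PD population is worsening of motor function". Section 9 assigns the monitoring of that concern to the MDS-UPDRS motor scale. Section 5.4.5 supplies a yardstick: "The minimally clinically important difference for improvement (-3.25) and worsening (4.63) on the MDS-UPDRS Motor was recently established".

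The analysis of the score is brief. The synopsis lists "Mean change in MDS-UPDRS motor from baseline to 12 weeks" among the safety and tolerability outcomes. Section 13.2 says "The mean change in MDS-UPDRS motor score and from baseline to 12 weeks will be calculated", and adds "Similar analyses will be done for all outcomes at 2 weeks, 4 weeks, and 8 weeks". For participants lost to follow-up, "last observation carried forward will be used". No SD, confidence interval, individual listing or proportion is specified for the motor score, and the value 4.63 appears in no analysis.

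Benefit is handled differently. HAM-A, CGI-I and PGI-I each have a planned proportion of improvers at 12 weeks.

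Motor harm could also surface elsewhere in section 13.2: in the primary count of those not completing on study drug, in the failures due to adverse events, in the number needing dosage reductions, and in the general tables ("Safety analyses will include tabulating adverse events by treatment group and severity and codifying the relationship to study drug"). The UKU scale is collected as well; section 5.4.7 notes that "The cardinal PD symptoms of tremor, rigidity, and hypokinesia are included".

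**The concern.** The harm in question happens to individuals, and a group mean lets improvement in some cancel worsening in others. The plan cites a value for important worsening and then plans no summary of the score that could show how many participants reached it.

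What is at stake is the motor evidence that the trial hands on. Section 1.2 gives the possible motor effect as the reason for a tolerability study before a larger efficacy trial. A report of little or no mean motor change would be read as reassurance, and the planned output would give the reader no means of checking it. If a threshold count is added only after the data are seen, the choice of cut-off and visit is open to question.

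**Working it through.** **Inputs from the documents.** Buspirone arm n = 21, calculated total 27 at 4:1, hence about 6 on placebo (section 13.1); cited worsening value 4.63 (section 5.4.5). The plan states no figure for the motor score that could be reproduced. The n = 21 does reproduce: rejecting at 7 or more failures, the exact binomial power at a true rate of 40% is P(X ≥ 7 | 21, 0.40) = 0.7998, the stated 80%.

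**Input assumed.** The documents give no SD for change in the motor score. A range of 4 to 10 points is used.

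**Step 1: can the mean hide worseners?**
- 4 participants at +6 and 17 at −24/17 = −1.41: mean = (4×6 − 17×1.41)/21 = 0.
- 4 participants at +5 and 17 at 0: mean = 20/21 = +0.95, far below 4.63.
- In both cases 4/21 = 19% exceed 4.63, with Clopper-Pearson 95% CI 5.4% to 41.9%.

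**Step 2: how many exceed 4.63 when the true mean change is 0?** With change ~ Normal(0, SD), P = 1 − Φ(4.63/SD) and the expected number is 21 × P.

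| Assumed SD | 4.63/SD | P(change > 4.63) | Expected of 21 | P(at least 3 of 21) |
|---|---|---|---|---|
| 4 | 1.16 | 0.124 | 2.6 | 0.49 |
| 5 | 0.93 | 0.177 | 3.7 | 0.75 |
| 6 | 0.77 | 0.220 | 4.6 | 0.87 |
| 8 | 0.58 | 0.281 | 5.9 | 0.96 |
| 10 | 0.46 | 0.322 | 6.8 | 0.98 |

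Sections 3.1 and 4.1 describe the figure of 35 differently (including screen failures; eligible participants). If all 35 were randomised, 35 × 4/5 = 28 would be on buspirone and the expected number would run from 3.5 to 9.0.

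This table cuts both ways. A mean of 0 does sit alongside several participants above 4.63, but much of such a count can be ordinary variation with no drug effect.

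**Step 3: can the placebo arm calibrate the count?** One of 6 gives 17% with exact 95% CI 0.4% to 64%. Calibration is weak.

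**Step 4: would counting a crossing at any visit be better?** Four in-person visits were simulated with mean change 0, the same SDs and an assumed correlation of 0.5 between visits. The proportion above 4.63 at least once is 31% at SD 4 and 62% at SD 10, about 6 to 13 of 21 with no drug effect. That roughly doubles the one-visit noise. Unscheduled visits, held on request or when judged necessary, would tend to push it higher.

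**Step 5: do the other planned outputs show the same thing?**
- Primary outcome: a participant who worsens but completes on any dosage (section 2.1) is not a failure.
- Dosage reductions and adverse-event failures: counted, but not by cause such as motor worsening.
- Adverse events: elicited by a non-specific question plus assessment of clinical features (section 9.3) and tabulated generally, with no link to the score.
- UKU: motor items collected, but section 13.2 plans no UKU analysis.
- Levodopa-equivalent dose: listed in the synopsis, also as a mean. Increases in PD medication are prohibited (section 3.2), so it cannot reliably reveal worsening.

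**The case against.** The strongest reply is that the plan already captures individual harm. Its primary outcome is a proportion of individuals, section 2.2 considered mean motor change as the primary outcome and rejected it, and section 13.2 counts adverse-event failures, dosage reductions and adverse events by arm and severity. This stands against a broad reading that motor worsening as such is analysed only by a mean. It does not meet the narrower point, which concerns the score: none of those outputs is motor-specific or tied to it.

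Three further inferences are tempting and are not supported.
- *Participants who worsen and stop drop out of the analysis.* The premature termination visit includes the motor examination, those who stop drug without withdrawing consent are still followed (section 8.5), LOCF is stated for those lost to follow-up, and weeks 2, 4 and 8 are analysed too. What remains is smaller: some of these scores may be taken after drug has stopped, when a reversible effect could have faded.
- *The drug could be declared tolerable on the strength of a flat mean.* The decision rule is 7 or more failures to complete on study drug. The mean does not enter it.
- *The protocol adopted 4.63 as its threshold.* It cites a published value and assigns it no role in the analysis.

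It is also fair to say that a count such as 19% would not by itself show harm, since it lies within the 12% to 32% expected from variation alone under the assumed SDs. That is a reason to report the count by arm with its interval and a caveat, not to omit it.

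**Conclusion.** The point holds for the MDS-UPDRS motor score. Its only planned summary is the mean change, which can be 0 or +0.95 while 4 of 21 (19%, exact 95% CI 5% to 42%) worsen by more than 4.63. That is arithmetic and needs no model. The expected counts of 2.6 to 6.8 of 21 at a true mean of 0 rest on a normal distribution and an assumed SD of 4 to 10.

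The consequence is limited to reporting. The sample size, primary test and decision rule are unaffected, and the count cannot separate drug effect from variation with about 6 on placebo. Its value is that it makes individual worsening visible under a rule fixed in advance. The addition is worth making, but the trial's primary conclusion does not depend on it.

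**What to change.** Keep the mean change and add to section 13.2 a descriptive secondary safety summary:

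- The number and proportion in each arm, with exact 95% CI, whose MDS-UPDRS motor score is more than 4.63 points above baseline at week 12 or, for those who stop early, at the last available assessment, including the premature termination visit.
- The same count at each scheduled in-person visit (weeks 2, 4, 8 and 12).
- A statement that some participants will exceed 4.63 by ordinary variation (about 12% to 32% at one visit if the SD of change is 4 to 10, an assumption), and that the small placebo arm calibrates this only weakly (1/6: 0.4% to 64%).
- A statement that a crossing at any visit, particularly with unscheduled visits included, will not be used as a headline measure.

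The cost is a few sentences and one table with wide intervals. The scores are already collected at every visit needed. Sample size, visits, treatment and the primary decision rule stay as they are.
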